### **5.4 Inclusion/Exclusion Criteria**

#### Inclusion criteria:

##### *Patients*

- Adults aged  $\geq 75$  years
- Advanced CKD as defined as having at least 2 outpatient measures of eGFR  $< 25$  ml/min/1.73m^2 separated by  $> 90$  days in the prior year and with at least 1 of these measures eGFR  $< 20$  ml/min/1.73m^2
- English-speaking

##### *Close persons*

- Adults aged  $\geq 18$  years
- Assists patient with their kidney disease care
- English-speaking

Exclusion criteria:

- Unable to complete the informed consent process

## 5.5 Randomization

Patients and their close person will be randomized together. We will use size 2 block randomization to assign patients to either: 1. The decision aid, or, 2. usual care (control). The study coordinator will be responsible for generating randomization codes using coin-toss.

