#### Study Team Personnel

*[name], Principal Investigator.* She will provide overall project leadership and supervision of study performance and progress. She will oversee all aspects of the study subject recruitment and follow-up, data collection and management, analyzing and interpreting data, and preparing study findings for publication and presentation. She will have access to protected health information.

*[name], Study Coordinator.* He will assist with project management and study coordination. He will not have access to protected health information.

*[name], Research Coordinator:* She will assist with contacting and recruiting subjects, obtaining subject informed consent, administering the intervention and surveys, interviewing subjects, and collecting and analyzing study data. She will have access to protected health information.

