## 5.6 Study Evaluations

The date of study enrollment will be the date that patient consent is obtained. Patients will be followed through patient's death, date of study withdrawal or 3-months after study enrollment, whichever is earliest.

Patients and close persons will each complete the following surveys and interviews at enrollment (T1), 2-week follow-up (T2) and 3-month follow-up (T3). All study procedures will be conducted by phone, and to maintain privacy, patients and close persons will complete procedures separately. After enrollment (T1), patients and close persons assigned to the intervention will be mailed *A Guide to Conservative Care* and will be given 2 weeks to review the *Guide*. The wording of surveys and interview guides will differ slightly to accommodate subjects who are patients and those who are close persons (see Study Materials). Patients who do not have a close person can still participate in the study and complete the following procedures.

Demographic questionnaire: At T1, patients and close persons will be asked 11 questions about their demographic background, including sex, age, race, prior education, total annual household income, current employment status, self-rated overall health, whether they had previously heard of dialysis or conservative care and sources of this information, relationship to patient (if close person), and whether they are the patient's surrogate decision-maker (if close person). This will take 3 to 5 minutes to complete.

Healthcare goals: At T1, T2 and T3, we will ask patients about their preference for either extending life or preserving comfort. Patients will also have the option of indicating that they are uncertain about which they prefer. Close persons will be asked a similar question about what they perceive the patients' healthcare goals are. This will take 1 to 3 minutes to complete.

Guide questionnaire: At T2, patients and close persons assigned to the intervention will be asked to complete a 4-item questionnaire on their experience with reviewing the *Guide*. This will take 10 to 15 minutes to complete.

Decisional conflict: At T1, T2 and T3, patients will be asked to complete the 16-item Decisional Conflict Scale to assess their preference for dialysis vs. conservative care. Close persons will be asked a similar question about what they would prefer for the patients. This will take about 5 to 8 minutes to complete.

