Post-intervention interview: At T2, patients and close persons assigned to the intervention will be invited to answer 4 open-ended questions on the usability of the decision aid. Interviews will be

audio-recorded then transcribed. We estimate that an interview will take 20 to 30 minutes to complete.

Late-intervention interview: At T3, patients and close persons assigned to the intervention will undergo a semi-structured interview to inquire how the decision aid prompted discussion of conservative care with others and their healthcare providers and the outcomes of those interactions. Interviews will take 20 to 30 minutes to complete and will be audio-recorded then transcribed.

Treatment status: At T3, we will ascertain whether patients had died, started dialysis and enrolled in hospice.

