## 5.7 Data Analysis

Feasibility and acceptability: As our primary aim, we will estimate the association of the intervention by the difference in patient-reported discussion of conservative care with their healthcare providers at T3. Based on prior work, the rate of patient-reported discussion of conservative care with their health care providers in usual care settings is approximately 29%. The target sample size (n=92) is estimated to provide 80% power (two tailed,  $\alpha=0.05$ ) to detect an absolute difference of 30% or more in rates of patient-provider discussion of conservative care between the intervention and control groups.

As part of our analysis of feasibility and acceptability, we will also calculate point estimates of completion rates and attrition rates and their 95% confidence intervals at T2 and T3. We will further assess user experience of the decision aid by performing a content analysis (an unstructured method of inquiry that facilitates discovery of previously unidentified factors pertaining to a phenomenon) of post-intervention interviews, coding for themes elucidating pros, cons and other considerations with using the decision aid to facilitate decision-making regarding conservative care with their healthcare providers.

Exploratory outcomes: We will assess change in knowledge on conservative care and confidence in making treatment decisions about conservative care (i.e., T3-T1 and T2-T1) based on scores on the Decisional Conflict Scale. To assess for goal concordant treatment decisions, we will measure the distribution of patients who rank life extension or comfort as their highest priority according to those who indicate on the Decisional Conflict Scale at T1, T2 and T3 that they opt for conservative care vs. dialysis. We will perform a content analysis of late-intervention interviews to ascertain detailed information about whether the decision aid prompted discussions on conservative care between patients, their close persons and providers, and code for themes reflecting actions taken by others and providers to subjects' interests and concerns regarding conservative care.

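### Fixed blocks of two, with arms visible to recruiting staff, make up to 46 of the 92 allocations known in advance and open a route to selection bias in the primary comparison.

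*Protocol*

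**What the plan says.** Section 5.5 (Randomization) sets three things. The unit is the patient with any close person: "Patients and their close person will be randomized together". The block length is fixed: "We will use size 2 block randomization to assign patients". The source of the sequence is named: "The study coordinator will be responsible for generating randomization codes using coin-toss". The ratio is 1:1 (abstract, Methodology).

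Section 4.0 (Study Team Personnel) separates two roles. Of the study coordinator, who makes the codes, it says "He will assist with project management and study coordination. He will not have access to protected health information". Of the research coordinator it says "She will assist with contacting and recruiting subjects, obtaining subject informed consent, administering the intervention and surveys"; she also interviews subjects and collects data.

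Section 5.6 (Study Evaluations) makes the procedures differ by arm. After T1, "patients and close persons assigned to the intervention will be mailed" the Guide. At T2 only that arm completes the Guide questionnaire and is invited to an interview. At T3, "patients and close persons assigned to the intervention will undergo a semi-structured interview".

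Section 5.7 (Data Analysis) gives the primary aim: "we will estimate the association of the intervention by the difference in patient-reported discussion of conservative care" with healthcare providers at T3. It is powered as a two-sided test at 5%.

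**The concern.** Randomization protects the comparison only if the person who approaches a patient cannot foresee that patient's arm. A fixed block of two removes this protection for every second patient. The block length is printed in the protocol, and the first arm of each pair becomes apparent from what staff do next for that patient. Having someone else generate the codes is sound practice, but it cannot hide an assignment that follows by subtraction from the previous one.

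The outcome is exposed to this. Whether a patient later reports a discussion of conservative care may depend on how open that patient is to the topic. If the upcoming arm is known, it could affect, even unintentionally, whom staff call next or how hard they pursue consent. The T1 data on prior awareness, healthcare goals and decisional conflict allow a partial check afterwards, but not of receptiveness that nobody measured.

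**Working it through.** **Inputs from the protocol.** 92 patients, 1:1, so 46 per arm; block size 2; usual-care rate 29%; detectable difference 30 points (29% vs 59%); two-sided alpha 0.05; power 80%.

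**1. The plan's own figure.** The unpooled normal approximation gives n = (1.960 + 0.842)² × (0.29×0.71 + 0.59×0.41) / 0.30² = 39.05 per arm. The continuity correction gives (39.05/4) × [1 + √(1 + 4/(39.05×0.30))]² = 45.47, hence 46 per arm and 92 in total. The sample size reproduces and is not in question.

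**2. Share of allocations that are certain.** In a 1:1 block of length 2m, the expected share forced by earlier assignments is 1/(m + 1). For m = 1 this is 1/2: 92/2 = 46 blocks with one forced assignment each, so 46 of 92. For known fixed blocks of 4 and 6 it is 33% and 25%.

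**3. Share that can be guessed correctly.** The best guess is right in a fraction [m + (2^(2m)/C(2m,m) − 1)/2] / (2m) of cases. For m = 1: [1 + (4/2 − 1)/2]/2 = 75%. For blocks of 4 and 6: 70.8% and 68.3%.

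**4. What steering could do.** The protocol has no figure for this, so the following are assumptions. There is no true effect and the rate is 29% in both arms. A share f of the known second slots is filled with patients whose outcome probability is 29% + d in Guide slots and 29% − d in control slots. Half of each arm sits in second slots, so the bias is ½·f·d + ½·f·d = f·d.

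Worked case, d = 10 points and f = ½: the bias is 5 points. The null standard error is √(2×0.29×0.71/46) = 0.0946, so the critical difference is 1.96 × 0.0946 = 0.185. With rates of 26.5% and 31.5% the actual standard error is 0.0945. The upper tail is 1 − Φ((0.185 − 0.05)/0.0945) = 7.6% and the lower tail 0.6%, together 8.2%.

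Simulation (200,000 runs, 46 per arm, pooled z-test) gives 4.9% without steering. With steering it gives (bias in points / two-sided type I error):

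| d | quarter of the 46 slots | half | all |
|---|---|---|---|
| 5 points | 1.3 / 5.2% | 2.5 / 5.8% | 5.0 / 8.2% |
| 10 points | 2.5 / 5.7% | 5.0 / 8.2% | 10.0 / 18.1% |
| 15 points | 3.7 / 6.8% | 7.5 / 12.4% | 15.0 / 35.1% |

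If only 23 of the 46 second slots are known and d = 15 points, steering half of those 23 gives 3.8 / 6.8%, and steering all of them gives 7.5 / 12.0%.

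**5. What longer, varying blocks would do.** These figures come from 1,500 simulated lists of 92, for someone who sees all past assignments and knows the possible sizes but not the size of each block.

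| Scheme | certain | guessed correctly | largest final difference between arms |
|---|---|---|---|
| Fixed 2 | 50% | 75% | 0 |
| Random 4/6 | 5.5% | 69.2% | 2 |
| Random 4/6/8 | 2.4% | 67.9% | 4 |

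Someone who also knew the actual length of each block would find about 28% of slots forced with 4/6 and 24% with 4/6/8. That would require access to the list.

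**The case against.** The arithmetic of the forced slots is not disputed; the case against concerns what follows from it. Bias arises only if the recruiter knows the previous arm in the sequence, knows it before approaching the next patient, and acts on it in a way related to the outcome. The protocol establishes none of these outright. It has no blinding statement, so visibility to staff is inferred from the procedures. The Guide is mailed only after T1, and recruitment takes a letter, a call about a week later and sometimes a further mailing and week. Two patients may therefore consent before the first arm of a pair is known. The protocol does not say whether the two sites share one sequence; if they do, the recruiter also needs the other site's last assignment.

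The room to steer is also limited. The principal investigator pre-screens the records, eligibility rests largely on age and laboratory values, and phone attempts after the letter are capped at three. Awareness, goals and decisional conflict are recorded only after consent. The 35% figure requires every second slot to be known and steered by 15 points in each direction, which is extreme; at the mild end the type I error stays near 5%. Finally, varying the block size alone lowers correct guessing only from 75% to about 69%.

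Most of this stands as a limit on size: 46 is a ceiling, and the bias may be small. None of it removes the defect. Nothing in the protocol conceals the second slot, and a pilot whose primary aim is a powered between-arm comparison needs unpredictable allocation. The modest fall in guessing is a reason to change the release procedure as well as the block size.

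**Conclusion.** The concern holds and should be fixed. The protocol itself fixes a scheme that forces 46 of 92 allocations, and its arm-specific procedures let recruiting staff learn the assignment that determines the next one. The 50% and 75% figures are exact for blocks of two when the previous assignment is known; fewer slots are exposed when consents overlap or staff do not see the latest assignment. The first patient of each pair remains unpredictable. The bias and type I error figures rest on assumed steering and show only what is possible. The sample size is unaffected.

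**What to change.** In section 5.5, replace the coin-toss blocks of two with a computer-generated list in permuted blocks of randomly varying size, for example 4 and 6, or 4, 6 and 8. Leave the block sizes out of the protocol version that recruiting staff use. Have the study coordinator, or another person outside recruitment, hold the list. State that each assignment is released only after the patient has consented and completed the T1 survey. All of these parts are needed, because longer blocks alone still leave many assignments guessable.

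The cost is minutes of programming and a minor amendment. The arms may end slightly unequal: by at most 2 patients with 4/6 blocks and 4 with 4/6/8 blocks in the simulated lists. A 48:44 split instead of 46:46 moves power for 29% vs 59% from 83.8% to 83.7% (pooled normal approximation without continuity correction, before attrition).

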### **Methodology**

We will recruit 92 patients aged 75 years and older with advanced CKD as defined as an estimated glomerular filtration rate  $<25$  ml/min/1.73m^2 from UW Medicine and VAPS. We will ask patients to invite up to 1 close person as defined as a relative or friend who assists them with their medical care to also participate in the study. We will randomize patients and their close persons in a 1:1 fashion to either usual care or receipt of the decision aid. Participants will complete all study procedures by phone and over a total of three phone study visits.

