### **4.0 Resources and Personnel**

#### Study Sites:

Study subjects will be recruited from the UW Medicine and VAPS in Seattle. Original study data collected with UW Medicine will be stored and at the KRI. Original study data collected at VAPS will be stored at the VACOIN. Deidentified UW patient data will be moved to VA Puget Sound in order to facilitate pooled analysis. All data analyses will occur at VACOIN. No VA data will be shared with the UW.

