## **9.0 Information Security and Data Storage/Movement**

UW patient data, including recruitment information, audio-recordings of interviews, interview transcripts, patient tracking information, and survey responses will be stored at the KRI in secure study folders. After recruitment and data collection, deidentified UW patient data will be moved to VAPS for final pooled analysis. All analysis will take place at VAPS.

The data flow for UW data is:

UW patient > VA and UW approved staff > UW servers > deidentified data into VA servers.

VA patient data, including recruitment information, audio-recordings of interviews, interview transcripts, patient tracking information, and survey responses, will be stored at VAPS in a secure J-drive study folder. No VA patient data will be shared with the UW, and all analysis will take place at VAPS.

The data flow for VA data is:

VA patient > VA and UW approved staff > VA servers

For both UW and VA data, interviews will be digitally audio-recorded and downloaded from recording devices to secure study folders using a USB fire cable. After audio-recordings have been saved, audio files will be erased from audio-recorders. Audio files of interviews will be labeled with study IDs and date of the interview only and will be accessible to the transcriptionist through the secure study folder. Transcripts of audio files will be saved as Microsoft Word format directly to secure study folders. The transcriptionist will not be permitted to save copies of audio files or transcripts onto personal computers or devices.

Survey study data will be assembled using structured forms designed in Microsoft Excel and saved in secure study folders. Data will be associated with study IDs only.

After deidentified UW data is moved to VAPS, all data collected at UW Medicine and VAPS will be stored on VACOIN access-protected servers on the J: drive. No VA data will be shared with the UW.

All research records, including the investigator's research records, must be retained until disposition instructions are approved by the National Archives and Records Administration (NARA) and are published in VHA's Records Control Schedule (RCS 10-1). (VHA Handbook 1200.05).

After all data are analyzed and manuscripts summarizing study findings are published (estimated 2029), all identifiable and crosswalk files will be destroyed.

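### Section 5.5 names no stratification by site, so if one list serves both UW Medicine and VAPS, balance of site mix between arms is left to chance: a minor point, cheaply fixed

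*Protocol*

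**What the plan says.** Section 5.5 (Randomization) contains the whole allocation scheme. Patient and close person are allocated together, and "We will use size 2 block randomization to assign patients to either: 1. The decision aid, or, 2. usual care (control"). It continues: "The study coordinator will be responsible for generating randomization codes using coin-toss". It mentions no stratification factor and does not say whether there is one list or one per site. The Methodology part of the abstract gives the ratio: "We will randomize patients and their close persons in a 1:1 fashion to either usual care or receipt of the decision aid".

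On sites, section 4.0 states: "Study subjects will be recruited from the UW Medicine and VAPS in Seattle". Section 9.0 adds that after data collection "deidentified UW patient data will be moved to VAPS for final pooled analysis".

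Section 5.7 makes the primary comparison the difference between arms in patient-reported discussion of conservative care with healthcare providers at T3. It gives a single usual-care figure, that "the rate of patient-reported discussion of conservative care with their health care providers in usual care settings is approximately 29" per cent, with no breakdown by site. It states: "The target sample size (n=92) is estimated to provide 80% power" for an absolute difference of 30 points, two-tailed at 0.05. The protocol gives no planned numbers by site.

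**The concern.** The primary outcome needs a provider to take part in a conversation, so its frequency may well depend on where the patient receives care. The protocol gives no ground for assuming that the two systems have the same rate.

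Blocks of two that run across sites guarantee equal arm totals and nothing more. When a pair holds one UW and one VAPS patient, the coin decides which site's patient receives the *Guide*. Such pairs accumulate, and the two arms of 46 can end with visibly different site mixes. If the sites' discussion rates differ, part of the observed difference then reflects site mix and not the *Guide*. The analysis can adjust for this, but the allocation cannot be rebalanced once patients are randomised.

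**Working it through.** **Inputs from the protocol.** 92 patients, 1:1, so 46 per arm; blocks of two, so 46 blocks; two sites; usual-care rate 29%; target difference 30 points, so 59% with the *Guide*; two-sided alpha 0.05.

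**Inputs not in the protocol (assumed).** VA share q of 20%, 30% or 50%. Site difference D in usual-care discussion rate of 10, 20 or 30 points around an overall 29%.

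**The protocol's own figure.** The pooled-variance formula for 29% against 59% at 80% power gives

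n = [1.96·√(2·0.44·0.56) + 0.8416·√(0.29·0.71 + 0.59·0.41)]² / 0.30² = (1.376 + 0.563)² / 0.09 ≈ 41.8, so 42 per arm (84 in total).

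With continuity correction it is 49 per arm (98). At 46 per arm, power is 83.8% by z test and 77.2% by Fisher's exact test. The stated 92 lies between these variants. I did not reproduce it exactly, it is not shown to be wrong, and nothing below depends on it.

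**Step 1: site mix under one list.** If patients arrive from either site at random, the between-arm gap in VA share has SD = √(2q(1−q)/46), the same as with no blocking. For q = 0.5 this is √(0.5/46) = 10.4 points, or √(46·2·0.25) = 4.8 patients. A simulation of 40,000 trials per setting agrees:

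| VA share | SD, formula | SD, simulated | Gap ≥ 10 points | Gap ≥ 20 points | 95th percentile of absolute gap |
|---|---|---|---|---|---|
| 20% | 8.3 | 8.4 | 24% | 1.4% | 17.4 |
| 30% | 9.6 | 9.5 | 30% | 3.0% | 19.6 |
| 50% | 10.4 | 10.4 | 35% | 4.7% | 19.6 |

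In patients, a gap of 10 points or more means at least 5 of 46, since 4/46 = 8.7 points and 5/46 = 10.9 points.

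**Step 2: shift in the primary difference.** Shift = gap in site share × D.

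| D | SD of shift | 95th percentile of absolute shift |
|---|---|---|
| 10 points | 0.8-1.0 | 1.7-2.0 |
| 20 points | 1.7-2.1 | 3.5-3.9 |
| 30 points | 2.5-3.1 | 5.2-5.9 |

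The ranges run over the three VA shares. The mean shift is zero.

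**Step 3: comparison with sampling error.** SE of the primary difference = √[(0.29·0.71 + 0.59·0.41)/46] = √(0.4478/46) = 9.9 points. This already contains the variation between sites. In the setting most favourable to stratifying (q = 0.5, D = 30 points), removing it leaves √(0.009735 − (0.30·0.1043)²) = √(0.009735 − 0.000978) = 9.4 points.

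**Step 4: error rates.** Without stratification, the unadjusted two-proportion z test has a simulated type I error of 4.8-5.2%. Its power at a 30-point effect is 82.7-83.3%. With site-stratified blocks of two, power is 83.1-84.3%. The largest gain in any one setting is 84.3 − 82.9 = 1.4 points, with a Monte Carlo standard error of √(2·0.83·0.17/40,000) ≈ 0.3 points. At D = 10 or 20 points the gain is below half a point. If allocation is stratified but the test ignores site, type I error falls to as little as 3.6% (q = 0.5, D = 30 points). The test is then conservative, which is why a site term belongs with stratification.

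**The case against.** The strongest reply is that this is good practice and not an error.

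- **One list is an inference.** Section 5.5 does not say that a single list spans both sites. Separate lists would fit the separate data storage in sections 4.0 and 9.0 equally well. This stands: the calculation applies only if one list is used, and if per-site lists are intended, one sentence settles the matter.
- **Differing sites.** A reader might infer that the two sites are known to practise very differently. The protocol does not say so. Both are in Seattle, eligibility and recruitment are common, all procedures are by phone, and the 29% is not split by site. The site difference is purely assumed; if it is zero, so is the shift.
- **Confounding.** A reader might also infer that site is confounded with treatment and the estimate biased. It is not. Under randomisation the imbalance is chance, its mean effect is zero, type I error is held, and the usual standard error already covers it.
- **Size.** Even the 95th-percentile shift of about 6 points is well under one standard error of 9.9.
- **Analysis detail.** A site term may already be in an SAP not seen here, and pooling the data files does not exclude one. The core request is therefore the change to 5.5.
- **Site-specific results.** These are not among the aims in section 3.0. With 92 patients over two sites and two arms there would be about 23 per cell at best, so stratification would not make them precise. I do not rest the point on this.

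What survives is narrower: the allocation section, which is protocol content, secures balance of arm totals but does not secure balance on the one grouping factor built into the design.

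**Conclusion.** The point holds as a minor one. As written, section 5.5 does not assure site balance. Under a single list, a gap in site mix of 10 points or more would arise in about a quarter to a third of trials. The likely consequence is small: a shift of about 1-3 points in the primary difference, beside a 30-point target. These figures rest on assumed VA shares of 20-50%, assumed site differences of 10-30 points, and arrival from either site at random. They show avoidable noise. They do not show an invalid comparison or an inadequate sample size.

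**What to change.** In section 5.5, state that a separate allocation sequence is generated for UW Medicine and for VAPS, with whatever block lengths are adopted. In section 5.7, or in the SAP if it covers this, include site in the primary comparison.

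The cost is a second list, one covariate and at most one incomplete block per site. The arms then differ by at most one patient at each site, about 2 points of site mix (1/46 = 2.2). Arm totals could differ by at most two patients, 47 against 45, if both sites end on an incomplete block. The benefit is assured site balance and up to about 1 point of power. The predictability of blocks of two is a separate matter that stratifying by site does not resolve. If patients have already been randomised from one list, the site term is the part that can still be applied to them.
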